Data on adherence to the treatment protocol will be collected twice weekly by research staff and reviewed weekly by the PI. Participants' compliance with treatment will be evaluated by the frequency of program use and actual minutes used. Monthly assessments will be made of protocol compliance, participant recruitment, accrual and retention, participant withdrawals, data quality and timeliness, risk-to-benefit evaluation, unanticipated problems (including adverse events), protection of confidentiality of information, and any other factors that may affect the study. In the case of adverse events, the date and time of onset and outcome, course, intensity, action taken, and causality to study treatment will be assessed by the PI. The PI will also review the outcome and adverse event data to determine whether a change to the anticipated risk-to-benefit assessment is required, and whether the study should continue as originally designed or should be revised. The IRB will be informed immediately of any adverse events and requests for modifications of the study protocol will be submitted quarterly. Confidentiality of the data and the results of monitoring will be protected.

A summary of the following assessments will be provided to the IRB annually at the time of study renewal or more frequently as required: list of research personnel who participated in the data and safety monitoring; the frequency of monitoring that took place during the renewal intervals and/or the dates on which data and safety monitoring was conducted; cumulative data related to unanticipated problems, including a determination of causality and a re-evaluation of the risk-to-benefit assessment; if applicable, pertinent scientific literature reports, therapeutic developments, or results of related studies that may influence the safety of study participants or the ethics of conducting the research study; outcome of reviews conducted to ensure participants' privacy and the confidentiality of research data; final conclusions regarding changes to the anticipated risk-to-benefit assessment of study participation; and final recommendations related to continuing, changing, or discontinuing the study.

20. Provisions to Protect the Privacy Interests of Participants

We will strictly adhere to HIPAA regulations to safeguard participants' privacy interests and their protected health information (PHI). We will ask permission to access and utilize any PHI, such as through the electronic medical record. All data will be kept confidential and will only be used for research purposes. The steps that will be taken to protect confidentiality and maintain the privacy of study participants will be outlined on the informed consent. These steps include: using a study number, rather than the participant's name, in data records, presentations, or publications; using a Certificate of Confidentiality; utilizing data use agreements for any future researchers who may want access to de-identified study data; not placing their research data into their electronic medical record; and not sharing any information about them with unauthorized individuals or without their written permission. If desired, participants will be able to revoke their permission for use of their PHI at any time during the study by contacting the study team in writing. We will help participants feel at ease with this study during the informed consent process and throughout the study by providing detailed information regarding the study purpose, research activities, their rights as a study

participant, their ability to choose not to answer any questions at any time, and their ability to discontinue participation at any time.

21. Economic Burden to Participants

There are no anticipated costs to patients for participating in this study. Participants will not be charged for any of the research activities.

22. Consent Process

The consent process will be completed by the project coordinator or principal investigator and will take place in person, in a private area of the SCD clinic, SC Foundation, research center, or remotely. After screening, eligible patients will receive information about the study. At least 15 minutes will be devoted to the consent discussion during which the study will be described to patients, they will be asked to explain what they understand about the study, and they will have an opportunity to ask questions and take any necessary time that is desired prior to making a decision regarding participation. Once an affirmative decision has been made, individuals will be asked to complete the informed consent and HIPAA authorization form. If there is a period of more than 60 minutes between the initial consent discussion and an affirmative decision to participate in the study, the project coordinator or principal investigator will review the consent discussion prior to obtaining consent. While study activities are being conducted remotely post-baseline, the project coordinator or principal investigator will remind the participants of their continued rights and assess their understanding of the study to ensure ongoing consent. This assessment of ongoing consent will be completed by the project coordinator or principal investigator during the check-ins that will be conducted via text messages or telephone calls and prior to conducting the post-intervention interviews. To minimize the possibility of coercion or undue influence, participants will be reminded that neither their study participation nor decision not to participate will influence their healthcare in any way.

In the event of any study changes or the need for remote consent, study staff will contact participants via telephone or Zoom (audio only) and they will be asked to provide verbal informed consent after the consent discussion takes place. As an option, e-consent may be utilized for completion of the informed consent form and electronic signature of consent may be used by study team members obtaining verbal informed consent. If participants request a copy of the revised consent form, then they will be emailed a link to the online consent form in REDCap. The email will not contain any information related to the participant's condition.

Non-English-Speaking Participants: Not applicable

The target population for this study consists of Black or African American adults with SCD. Members of this population are proficient with the English language.

Participants who are not yet adults (infants, children, teenagers): Not applicable

Cognitively Impaired Adults: Not applicable

Adults Unable to Consent: Not applicable

Waiver or Alteration of Consent Process (consent will not be obtained, required information will not be disclosed, or the research involves deception): Not applicable

23. Setting

The research team will identify and recruit potential participants at the Georgia Comprehensive Sickle Cell Center at Grady Memorial Hospital (Grady) in Atlanta, Georgia and the James R. Clark Sickle Cell Memorial Foundation (SC Memorial Foundation) in Columbia, South Carolina. After baseline, research procedures will be conducted remotely while participants are at home or may be conducted in a private area of the research center (Nell Hodgson Woodruff School of Nursing at Emory University) or the SC Memorial Foundation if in-person activities are necessary.

24. Resources Available

Of the 1100 adults annually served by the SCD center, over 50% are ages 18–40 and experience chronic pain, and approximately 30 individuals in this age range are seen in the SCD clinic weekly.^{71,72} In addition, the SC Memorial Foundation has a client roster of approximately 400 adults. Therefore, it is feasible to recruit the required number of suitable participants (n = 50).

Medical resources (such as Grady or local area hospitals) and psychological resources (such as the Georgia Crisis and Access Line, the South Carolina Crisis Response Dispatcher, or local area hospitals) will be available to participants to address any unanticipated consequences of this research. A clinician (clinical psychologist) will also be available to provide additional assistance if needed to manage participants who score in the upper range of the depression measure or disclose suicidal ideation during the study.

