After screening patients for eligibility using the inclusion and exclusion criteria, the project coordinator will describe the study to and seek participation from eligible individuals. Participants will be informed that the purpose of the study is to test a pain management intervention that will be delivered in two different ways, but their group allocation will not be revealed. The study conditions will be presented as adjuncts to standard care and there will be no restriction on using other pain management methods. After patients provide written, informed consent or verbal informed consent, they will complete baseline study questionnaires. Once enrolled, participants may self-withdraw at any time, or they may be withdrawn if they fail to or are unable to comply with study procedures. In that case, recruitment will resume and continue until the target number of participants is reached.

After completing baseline questionnaires, participants will be randomized 1:1 to receive either EaseVRx or control. Only individuals meeting the eligibility criteria for VR will be assigned to the VR group. Participants will receive study materials and instructions for home use before being followed prospectively for 8-weeks with follow-up at 12 weeks. Participants in the VR group will receive an all-in-one, non-tethered VR headset (Pico G24K headset with AppliedVR breathing amplifier) that is pre-loaded with EaseVRx. They will receive education and hands-on experience with the VR headset to ensure safe and comfortable device use at home. Access to technical support will also be provided. Each week, participants will be asked to complete 7 assigned modules, averaging 5 minutes in duration and ranging from 2 to 16 minutes in

Protocol Title: Home-Based Intervention for Chronic Pain in Adults with Sickle Cell Disease (HIPAS)

duration, for a total of 56 modules across the program. The order of the modules is fixed but participants can repeat modules as desired. Participants in the control group will be asked to use the audio only version of EaseVRx, which excludes references to visual content, to complete 7 sessions weekly. They will receive an electronic link to the recordings on SoundCloud (a music streaming platform) where they can choose to stream or download the audio recordings on their smartphone, laptop, or desktop computer.

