	Adult Sickle Cell Quality of Life Measurement Information System (ASCO-Me SM) SCD Medical History Checklist	x				
	Medical record data collection form	x				
Pain and self-management of pain	Pain diary	x	x	x	x	x
Pain and disability	Chronic Pain Grade Questionnaire	x		x	x	x
Pain catastrophizing	Pain Catastrophizing Scale	x		x	x	x
Chronic pain acceptance	Chronic Pain Acceptance Questionnaire	x		x	x	x
Chronic pain self-efficacy	Chronic Pain Self-Efficacy Scale	x		x	x	x
Health literacy	BRIEF Health Literacy Screening Tool	x		x	x	x
Executive function	Behavior Rating Inventory of Executive Function ®—Adult Version (BRIEF-A)	x		x	x	x
Anxiety	PROMIS® Emotional Distress - Anxiety	x		x	x	x
Depression	PROMIS® Emotional Distress - Depression	x		x	x	x
Social support	Social Support Questionnaire	x		x	x	x
Sleep	ASCO-Me SM Sleep Impact Short Form	x		x	x	x
Functional activities of daily living	ASCO-Me SM Pain Short Form	x		x	x	x
Quality of life	ASCO-Me SM Short Forms: Pain Episodes, Emotional Distress, Social Functioning, Stiffness	x		x	x	x
Screening prior to treatment	Questionnaire to Screen for Cybersickness or Digital Motion Sickness	x				
	Virtual Reality Sickness Questionnaire		x	x	x	
Participant engagement and acceptability	Program usage statistics (automatically recorded by the VR program) and completion of study questionnaires		x	x	x	
Study retention	Program usage statistics (automatically recorded by the VR program) and completion of study questionnaires	x	x	x	x	x
Participant satisfaction, and participant needs and preferences for tailoring the program	Semi-structured interview guide for qualitative sessions					x

7. Data and Specimen Banking

Not applicable

8. Sharing of Results with Participants

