De-identified study data may be placed into public databases where, in addition to having no direct identifiers, researchers will need to sign data use agreements before accessing the data. De-identified findings may also be posted on the project website. This can provide a forum for obtaining feedback from research participants and their family members or caregivers, healthcare providers, and visitors such as professionals and non-professionals. In addition, we will share study findings in accordance with the NIH policy. Electronic copies of publications arising from the proposed study will be deposited in PubMed Central with proper tagging of data to ensure online discoverability and accessibility.

9. Study Timelines

- Enrolled individuals will participate in this study for 8 weeks, with follow-up at 12 weeks.
- We anticipate enrolling all participants within the first six months of the study.
- We estimate a two-year study period for completion of all study activities.

10. Inclusion and Exclusion Criteria

Inclusion Criteria

Black adults, ages 18–50 years; diagnosis of SCD; chronic non vaso-occlusive pain experienced > 3 days per week on average for > 6 months; ability to wear a VR head-mounted display and move head in cervical rotation, extension, and flexion; sufficient fine motor control to operate VR equipment such as a controller; and ability to read, write, and understand English.

Exclusion Criteria

1. Conditions: Co-morbidities that may influence pain perception; diagnosis of epilepsy or susceptibility to seizures, migraines, or other neurological disorders that may prevent VR use, and/or other medical conditions due to which individuals are predisposed to nausea and dizziness; susceptibility to claustrophobia, motion sickness or cybersickness (digital motion sickness); history of blackouts; hypersensitivity to flashing lights or motion; lack of stereoscopic vision; severe visual or hearing impairment; inability to operate VR equipment (such as inability to turn head or use hands to operate external controller); and/or injury to the eyes, face, head, or neck that prevents comfortable VR use.

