We anticipate accruing a total of 40 participants locally to achieve a total of 50 participants from both recruitment sites. To obtain a final sample size of $n = 40$, we will enroll $n = 70-90$ to account for dropout or non-completion. We expect to screen approximately 144 individuals to achieve a total accrual of 40 participants.

13. Recruitment Methods

After obtaining approvals, active and passive recruitment for this study will take place at the Georgia Comprehensive Sickle Cell Center at Grady Memorial Hospital (Grady) in Atlanta, Georgia and the James R. Clark Sickle Cell Memorial Foundation (SC Memorial Foundation) in Columbia, South Carolina. Active recruitment by the project coordinator will involve the weekly screening for eligibility and enrollment of adults who receive care in the sickle cell clinic at Grady and who are served by the SC Memorial Foundation. Potential participants will be identified and screened for eligibility, using the inclusion and exclusion criteria, by conducting an initial review of medical records or obtaining patient report. Active recruitment may also occur through healthcare providers and community health workers who inform potential participants about the study, either in person or via mailed opt-in/opt-out letters, if necessary (see attached document), and provide them with contact information for the project coordinator or principal investigator (PI). Passive recruitment will occur via the use of flyers placed at the sickle cell clinic and SC Memorial Foundation to inform potential participants about the study. If necessary, these flyers may also be published on social

Protocol Title: Home-Based Intervention for Chronic Pain in Adults with Sickle Cell Disease (HIPAS)

media including Instagram, Facebook, and Twitter or via a website developed specifically for the study. Interested individuals will be invited to contact the program coordinator or PI, using the contact information provided on the flyers (see attached document), for further information. In the event of any enrollment shortfalls, we will do the following to achieve recruitment goals: consider loosening the exclusion criteria, expand the study to an additional sickle cell clinic, utilize area resources to increase the efficiency of participant enrollment, and/or extend the recruitment period.

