Study recruitment and data collection will occur in person, in a private area of the SCD clinic, SC Foundation, or research center, or remotely while participants are at home. All potential participants will be screened for eligibility using the inclusion and exclusion criteria. Eligible participants will receive information about the study, and will be asked to complete an informed consent, or a verbal informed consent, and a Health Insurance Portable and Accountability Act (HIPAA) authorization form. The informed consent document states that participants may choose to not answer any question or may end their participation in the study at any time. During the interviews or focus group sessions, participants will be reminded that their participation is voluntary and that they may stop at any time if they are uncomfortable with any questions.

Prior to treatment, we will ask potential participants screening questions, using the Questionnaire to Screen for Cybersickness or Digital Motion Sickness, to determine whether they have had or may have any of these issues. If so, they will not be considered eligible for participating in the VR group only. If they are considered eligible for the VR group (provided no affirmative responses to the screening questions), then participants will remotely complete the Virtual Reality Sickness Questionnaire before each use of the VR program. Only individuals without severe symptoms, as reflected on the questionnaire, will move forward with VR use. These individuals will also be asked to remotely complete the Virtual Reality Sickness Questionnaire after each use of the VR program. Participants who are randomized to the VR group will be instructed to adhere to the usage recommendations specified by the VR program's manufacturer. In addition, VR participants will be instructed not to use the VR device while ambulating, and that they should use the headset a maximum of 3 times per 24-hour period (morning, noon, and evening) for not more than 30 minutes consecutively. During the 8-week, home VR

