use period, we will use telephone calls or text messages to conduct weekly study assessments of adverse events. Users of the VR program who experience adverse events are free to suspend or halt VR use at any time by removing the headset. This can remedy the VR side effects. In addition, the VR program offers a range of experiences to allow participants to identify lower risk experiences. For participants who experience adverse events, we will discontinue their study participation and refer them to a member of the medical team as needed for any medical follow-up. All participants will have the ability to withdraw from the study at any time.

At this time, the risks of VR during pregnancy (i.e., risks to the pregnant woman, the embryo, or fetus) are not yet known. Therefore, to protect against possible side effects, women who are pregnant or nursing a child will not participate in exposure to VR. Female participants will be asked to immediately notify study staff if they become pregnant during the study. In that case, they will not be exposed to VR but may continue with other remaining study activities.

Active suicidal ideation, as documented in the patient's medical records, is one of the exclusion criteria. Among eligible participants, we will assess depression with the PROMIS® Emotional Distress – Depression (Short Form) at baseline, mid-treatment, and monthly post-treatment via remote data collection. This measure does not include a suicide item. To manage participants who score in the upper range of the depression measure or disclose suicidal ideation, we will utilize the following protocol.

- a. At the end of the survey in the questionnaire management system, participants will see this statement: *If you are feeling distressed or you are having thoughts of hurting yourself, please call 911, call the 24-hour Georgia Crisis and Access Line at [name], call the South Carolina 24-hour Crisis Response Dispatcher at [name], go to Grady Memorial Hospital or your local hospital, or call your healthcare provider.*

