Electronic methods, including REDCap and Microsoft Office, will be used to organize and manage data collected from this study. A data collection log will be used to enable tracking of data collection activities. Data collection logs will specify what data are to be collected for each participant, using which instruments, with expected and actual dates of data collection. Detailed reports of completed instruments listed by participant identification number will be generated for program management purposes; for instance, to plan for conducting focus group sessions or individual interviews.

Data Analysis

Data will be collected and managed by using REDCap. All quantitative data will be verified and periodic quality assurance checks of data entry will be performed. Once finalized, data will be exported from REDCap into the Statistical Package for the Social Sciences (SPSS Version 26) for statistical analysis. We will code the surveys manually and evaluate their psychometric properties in the sample. Initial data analysis will include descriptive statistics (e.g., means, standard deviations, frequencies, and percentages) on sample characteristics and outcomes at each time point. To ensure balance in participants' characteristics by intervention group at baseline, we will compare the sociodemographic and clinical characteristics (e.g., age, gender, disease severity, and comorbidities) of participants using t-tests or chi-square tests as appropriate. Any differences across treatment groups will be accounted for in subsequent analysis. We will also evaluate any attrition according to participants' characteristics. We will assess distributional assumptions of outcomes and perform appropriate transformations to remedy any violations. We will minimize missing data by monitoring data regularly and implementing successful methods for obtaining follow-up data. When data cannot be collected, sensitivity analysis will be performed to evaluate the impact of missing data on results. We also plan to use the restricted maximum likelihood (REML) method for model estimation whenever possible to minimize the impact of missing data. All outcomes will be compared among participants in both arms. All statistical tests will be two-sided and intent-to-treat procedures

Protocol Title: Home-Based Intervention for Chronic Pain in Adults with Sickle Cell Disease (HIPAS)

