will be employed. Additionally, all analyses will include sex (male vs female) as a biological variable to assess differences in outcomes within each group.

Number and percent will be used to summarize the primary feasibility measures while content analysis will be used to summarize the secondary feasibility measures. Optimal treatment will be determined by correlations among the engagement outcomes and measures of preliminary efficacy. We will use mixed-effects models to test whether the outcomes differ across the treatment group over time (from pre- to post intervention). Depending on the type of outcome (continuous or categorical), linear or generalized mixed effects models will be used, respectively. In this approach, each participant is treated as an experimental unit with repeated observations over time. The model will include fixed effects of time, intervention group, and time x intervention group interaction, and assume an unstructured variance-covariance matrix to describe the covariance structure. We will adjust for any baseline group differences in participant characteristics. A significant interaction effect will indicate significant differences in outcomes by treatment groups over time. We will select the most parsimonious model using Akaike information criterion (AIC) and Bayesian information criterion (BIC). Hypotheses tests based on specific contrasts in the mixed model and the interaction term between time and intervention group will be performed to test whether subjects in the intervention group demonstrated improved outcomes compared to the control group. The model-based estimates of the outcome measures for the two treatment groups at each time point will be used to estimate effect sizes for future studies.

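### Sections 6 and 15 let someone who fails the cybersickness screen stay in the trial for audio only, while Section 10 excludes them; the permissive wording could bias the VR-versus-audio comparison

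*Combined protocol and SAP*

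**What the plan says.** Four parts of the protocol bear on who may enter which arm.

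- **Section 6, Procedures for Participants.** Participants complete baseline questionnaires and are then randomized 1:1. The next sentence reads: "Only individuals meeting the eligibility criteria for VR will be assigned to the VR group".
- **Section 15, Procedures to Reduce Risks.** Before treatment, people are asked whether they have had, or may have, cybersickness problems. "If so, they will not be considered eligible for participating in the VR group only". VR eligibility requires that no screening question is answered yes. The same section states that "women who are pregnant or nursing a child will not participate in exposure to VR".
- **Section 10, Exclusion Criteria.** The list for the whole trial includes "susceptibility to claustrophobia, motion sickness or cybersickness (digital motion sickness". Being able to wear a VR headset is an inclusion criterion for everyone. Pregnancy is excluded; nursing is not mentioned.
- **Sections 13 and 6 (Table 1).** Eligibility under Section 10 is first checked "by conducting an initial review of medical records or obtaining patient report". The "Questionnaire to Screen for Cybersickness or Digital Motion Sickness" is a separate instrument, scheduled at baseline.

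On analysis, Section 18 (Data Analysis) says "All statistical tests will be two-sided and intent-to-treat procedures" will be employed. It plans a mixed model with a time-by-group interaction and adjustment for baseline differences. It adds that "model-based estimates of the outcome measures for the two treatment groups at each time point will be used to estimate effect sizes" for later studies.

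**The concern.** Sections 6 and 15 describe eligibility for one arm; Section 10 describes eligibility for the trial. They cannot both govern a person who screens positive at baseline. If Section 10 governs, that person leaves. If Sections 6 and 15 govern, that person stays and can only be given audio.

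Under the second reading the audio arm holds a subgroup that by construction is absent from the VR arm. The participants eligible for both arms are still compared at random, but the analysed arms are not, because audio contains additional people placed there by a baseline characteristic. Susceptibility to cybersickness may or may not be related to pain catastrophizing (the primary measure) or to its course; the documents do not say.

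At stake are the effect sizes. The revision history gives their estimation as a main purpose of this pilot, and Section 18 passes them on to future studies.

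**Working it through.** **1. Can such a person exist under the text?** The two checks differ. The Section 10 check uses records or self-report. The Section 15 check is a questionnaire that also covers possible problems, and any yes bars VR. A person can pass the first and fail the second. Nothing says that this person is then removed, kept out of the comparison, or analysed in a particular way. Section 15 times the screen only as before treatment. Table 1 and Section 6 together suggest that it precedes randomization, but no sentence says so.

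**2. The plan's own sample-size figure.** The revision history (entry of 10/28/2022) states d = 0.9 with 40 participants, 80% power and a 5% level; Section 18 makes tests two-sided. Normal approximation: n per arm = 2(1.960 + 0.842)²/0.9² = 19.4, so 20 per arm and 40 in total, with power 0.81. With a two-sample t-test, 20 per arm gives power 0.79 and a detectable d of 0.909. The figure reproduces.

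**3. Composition of the arms.** Let f be the share eligible for audio only. It is not in the documents, so it is an assumption. If all of them go to audio and the rest are split 1:1:

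- VR fraction = (1 − f)/2; audio fraction = (1 − f)/2 + f = (1 + f)/2
- audio-only share of the audio arm = f ÷ (1 + f)/2 = 2f/(1 + f); share of the VR arm = 0

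**4. Bias.** Let g be the difference, in SD, between audio-only and eligible participants (also an assumption). The audio mean shifts by g × 2f/(1 + f).

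| f | Audio-only people in 40 | VR / audio | Share of audio | Bias, g = 0.25 | Bias, g = 0.5 |
|---|---|---|---|---|---|
| 2.5% | 1 | 19.5 / 20.5 | 4.9% | 0.012 | 0.024 |
| 5% | 2 | 19 / 21 | 9.5% | 0.024 | 0.048 |
| 10% | 4 | 18 / 22 | 18.2% | 0.045 | 0.091 |
| 20% | 8 | 16 / 24 | 33.3% | 0.083 | 0.167 |

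The lower rows are more plausible if Section 10 is largely enforced; 20% is an upper illustration.

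**5. Which estimate is affected.**

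- *Time-by-group interaction.* If g is a stable difference in level, it is present at baseline and at follow-up and cancels. If g is a difference in change, the table applies.
- *Group difference at a single time point.* A level difference carries through in full.

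A simulation checked this algebra: n = 40, pre/post correlation 0.6, no treatment effect, 40,000 runs, and 2, 4 or 8 audio-only people. A stable 0.5 SD level difference gave week-8 group differences of 0.049, 0.091 and 0.168, and differences in change of 0.000, −0.002 and 0.000. A 0.5 SD difference in change gave differences in change of 0.047, 0.089 and 0.167. It says nothing about the true f or g.

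**6. Effect on a test.** With no true effect and a nominal 5% two-sided t-test, the rejection rate is 5.2% (g = 0.25) or 5.9% (g = 0.5) at f = 10%, and 5.7% or 8.0% at f = 20%.

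**7. Can the planned safeguards help?** Adjustment for measured covariates may reduce the bias. It cannot stand in for VR eligibility, because no ineligible person is in the VR arm to compare with. Intent-to-treat preserves a random assignment, but Section 6 makes the assignment itself depend on eligibility.

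**The case against.** The strongest reply is that Section 10 already removes everyone susceptible, so the VR-only clause applies to nobody, f is zero and the bias is zero. Section 6 opens with screening against the full criteria, and its sentence on assignment may be only a safety statement that nobody unsuitable receives a headset. No passage says outright that such people are sent to audio. This stands as a possible reading. But it leaves the Section 15 clause with no purpose, and it does not cover someone who first answers yes on the baseline questionnaire.

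Second, intent-to-treat would protect the comparison if a person were randomized to VR, then diverted to audio, and analysed in VR. That is correct: the formula above would not apply, and the cost would be a diluted contrast instead. The protocol does not describe this route; its wording makes VR assignment conditional.

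Third, the magnitude rests wholly on assumed values and is small. At f = 5% and g = 0.5 the bias is 0.048 SD against a standard error of √(1/19 + 1/21) = 0.317, or about 0.15 standard errors. Head counts in 40 analysed also assume equal completion, although observed non-completion was more than double the planned 20%. All of this stands and limits the importance of the point.

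Fourth, the per-time-point estimates could be turned into effect sizes for change, where a stable level difference cancels. Section 18 does not say which will be used, so the exposure remains.

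Finally, nursing is a separate gap: Section 15 places no nursing woman in audio. It matters here only because it is a second VR-only restriction with no counterpart in Section 10.

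**Conclusion.** The concern holds: the protocol is wrong as written and should be corrected. The contradiction between Section 10 and Sections 6 and 15 is certain. The bias is conditional on the permissive wording being followed for at least one participant.

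Under assumed shares of 2.5% to 20% and an assumed 0.5 SD difference, the bias is 0.02 to 0.17 SD, and half that at 0.25 SD. It reaches the per-time-point effect sizes through a difference in level, and the time-by-group test only through a difference in change. Its direction is unknown. At the lower shares it is minor beside a detectable d of 0.9, but a larger sample would not remove it. If Section 10 was fully enforced before randomization, it is zero.

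**What to change.** **Protocol text.** Reconcile Sections 6 and 15 with Section 10. State that the cybersickness screen is completed before randomization and that only participants eligible for both arms are randomized. Remove or reword the two sentences that make eligibility specific to the VR group. The sponsor must also reconcile the nursing wording in Section 15 with Section 10; however that is settled, anyone not eligible for both arms stays outside the randomized comparison.

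**Participants already enrolled.** Flag VR eligibility from baseline status, not from the arm received, and check the screen date against the allocation date. Limit between-arm comparisons to participants eligible for both arms. Report any audio-only placements, with their number, as a separate non-randomized cohort. If there are none, say so.

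**Cost.** Wording and one database flag; the screen is already collected. The comparison set shrinks slightly. Within 40 analysed, at 80% power and a two-sided 5% level (two-sample t-test), removing audio-only participants changes the detectable d as follows:

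- 2 removed: 0.910 (19/21) to 0.934 (19/19)
- 4 removed: 0.914 (18/22) to 0.961 (18/18)
- 8 removed: 0.928 (16/24) to 1.024 (16/16)

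If nobody was placed this way, nothing is lost.
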